8.6.1 Plans for Interim Analysis

There are no plans for interim analyses with an intent to stop the registry early or to adapt the registry design or planned number of patients.

8.6.2 Plans for Final Analysis

Final analysis will be conducted after the database lock takes place for the study.

8.7 Sensitivity Analyses

No sensitivity analysis will be conducted.

8.8 Subgroup Analyses

Subgroup analyses will be performed for the following variables: Type of disease (CRLM, HCC, Cholangiocarcinoma, Other) and NeuWave ablation confirmation software use. Subgroup analysis will be conducted for the primary endpoints that include technical success, technique efficacy, and target lesion recurrence.

8.9 Assessment of Site Homogeneity

Not applicable.

8.10 Exploratory Analyses

Logistic regression analysis will be utilized to explore the relationship between dichotomous clinical outcomes (technical success and technique efficacy) and ablation procedure, patient, and provider parameters. Significance level of 0.2 will be used for variable selection in a regression model. Cox proportional hazard model will be used for time to event analyses for target lesion recurrence to explore the relationship with ablation procedure, patient, and provider parameters.

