Secondary Endpoints	
 • Secondary efficacy rate • Regional recurrence rate at a separate location in the liver • Recurrence-free survival • Overall survival • Economic impact of ablation • Incidence of reportable Adverse Events/Serious Adverse Events (AEs/SAEs) • Numeric Pain Rating Scale • Quality of Life Questionnaires (QLQ-C30 and QLQ-HCC18)
Inclusion Criteria	
 1) Patients who underwent or are scheduled to undergo a microwave ablation of one or more liver lesions with the NEUWAVE Microwave Ablation System per the device's Instructions for Use (IFU). 2) Patients with signed informed consent (or waiver approved by IRB/EC) who are willing to comply with the assessment schedule, and willing to have data included in the database. 3) Patients ≥ 22 years old at the time of informed consent (or waiver approved by IRB/EC).
Exclusion Criteria	
 1) Patients with a life expectancy of less than 1 year, in the opinion of the treating physician. 2) Use of microwave ablation purely as a transection tool, rather than focused liver lesion ablation. 3) Patient is currently participating, or planning to participate, in another NeuWave/Ethicon-funded clinical trial or registry studying microwave ablation in the liver. Note: roll-over patients from previous NeuWave trials are permitted.
Safety Assessments	Patients will be assessed per the Schedule of Assessments for AEs that are procedure- or device-related and all SAEs.

Statistical Analysis	
Categorical variables will be summarized descriptively by frequencies and associated percentages. Continuous variables will be summarized descriptively by number of patients, mean, standard deviation, median, minimum, and maximum. Confidence intervals will also be provided for procedure-related variables.
 
Models will be built to explore the relationship between technical success, technique efficacy, and secondary efficacy rate, and ablation procedure, patient, and provider parameters. Time to event analyses will be used for target lesion recurrence rate, recurrence-free survival, and overall survival.

Interim Analysis	
There are no plans for interim analyses with intent to stop the registry early or to adapt the registry design or planned number of patients.

Determination, if DSMB required	
There will not be a DSMB utilized for this observational registry.

Schedule of Assessments Table:

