17.5 Primary Endpoint and Associated Hypotheses

This protocol does not have a single primary endpoint and there are no associated hypotheses. Rather, there are several patient-level outcomes of interest that will be investigated through statistical modeling to estimate the relationship between these outcomes and various patient, provider, and ablation-specific parameters. These patient-level outcomes of interest include: technical success, technique efficacy, secondary efficacy rate, target lesion recurrence rate, recurrence-free survival, and overall survival.

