17.9 Analyses to be Conducted

Categorical variables will be summarized descriptively by frequencies and associated percentages. Continuous variables will be summarized descriptively by number of patients, mean, standard deviation, median, minimum, and maximum. Confidence intervals will also be provided for procedure-related variables.

Disposition of Registry Patients

Patient disposition will be summarized using counts and percentages. The number and percentage of patients completed and discontinued along with the specific reasons for discontinuation will be tabulated.

Demographic and Baseline Characteristics

Summary statistics will be provided for patient demographics and pre-operative ablation characteristics.

Primary and Secondary Endpoint Analyses

Regression analysis methodologies will be utilized to explore the relationship between dichotomous clinical outcomes (technical success, technique efficacy, and secondary efficacy rate) and ablation procedure, patient, and provider parameters. Time to event analyses will be used for target lesion recurrence, regional recurrence rate, recurrence-free survival, progression free survival, and overall survival.

Complete details regarding all analysis methodologies including approaches to handle multiple lesions per patient, variable selection techniques, data reduction techniques given the number of potential independent variables, as well as subgroup analyses of interest will be specified in the SAP.

The number and percentage of patients achieving technical success will be summarized and a 95% confidence interval will be provided. A similar summary will be provided for technique efficacy, as well as for the primary and secondary efficacy rates, as previously defined.

Target lesion recurrence rates at each post-ablation scheduled visit will be estimated using the Kaplan-Meier method and 95% confidence intervals will be provided. A similar summary will be provided for the 5-year overall rate. Similar summaries will also be provided for regional recurrence rate, overall and progression-free survival rates for the entire observation period from the ablation procedure date through 5 years of follow-up.

Scores from the EORTC QOL questionnaires and Numeric Pain Rating Scales will be summarized with methodology consistent to the recommendations of the specific survey. Additional endpoints will be summarized with descriptive statistics.

Plans for Interim Analysis

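### SAP 8.10 models only three of the six outcomes that protocol 17.5 says will be modelled; secondary efficacy, recurrence-free survival and overall survival have no covariate model, and no reason is given

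*SAP*

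**What the plan says.** Protocol 17.5 sets no hypotheses. In their place it states that several outcomes will be "investigated through statistical modeling to estimate the relationship between these outcomes and various patient, provider, and ablation-specific parameters", and it lists them: "These patient-level outcomes of interest include: technical success, technique efficacy, secondary efficacy rate, target lesion recurrence rate, recurrence-free survival, and overall survival".

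For secondary efficacy the commitment appears twice more. The statistical paragraph of the protocol summary (section 4.0) says "Models will be built to explore the relationship between technical success, technique efficacy, and secondary efficacy rate" and the three groups of parameters. Section 17.9 applies regression to "dichotomous clinical outcomes (technical success, technique efficacy, and secondary efficacy rate) and ablation procedure, patient, and provider parameters".

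SAP 8.10 gives the corresponding list without secondary efficacy: "Logistic regression analysis will be utilized to explore the relationship between dichotomous clinical outcomes (technical success and technique efficacy". For outcomes measured as time to event, it says "Cox proportional hazard model will be used for time to event analyses for target lesion recurrence to explore the relationship" with the same groups of parameters. It names no other outcome.

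**The concern.** The primary objective in both documents (protocol 6.1, SAP 1.1.1) is to understand how selected parameters affect procedure and patient outcomes. No hypothesis is tested, so the covariate models are the analysis that most directly answers that objective. If an outcome has no model, the objective is not addressed for it in the plan.

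The registry plans five years of follow-up and collects procedure, patient and provider data. If the SAP is followed as written, none of these data would be related to RFS, OS or the success of repeat ablation. Any such model would then be chosen after the data are available, with covariates and model form open to choice.

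**Working it through.** **Step 1. Compare the two lists.** Inputs: protocol 4.0, 17.5 and 17.9; SAP 8.5, 8.6, 8.8, 8.10 and 8.14.

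| Outcome | To be modelled per protocol 17.5 | Covariate model in SAP 8.10 | Other analysis in the SAP |
|---|---|---|---|
| Technical success | Yes | Logistic | Clopper-Pearson interval; subgroups |
| Technique efficacy | Yes | Logistic | Clopper-Pearson interval; subgroups |
| Target lesion recurrence | Yes | Cox | Kaplan-Meier and cumulative incidence; subgroups |
| Secondary efficacy | Yes (also 4.0 and 17.9) | None | Clopper-Pearson interval |
| RFS | Yes | None | Kaplan-Meier |
| OS | Yes | None | Kaplan-Meier |

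The protocol has 6 outcomes and the SAP models 3 of them, so 6 − 3 = 3 are missing. RFS and OS are two of the six, and secondary efficacy is the third missing outcome.

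**Step 2. Look for the missing models elsewhere in the SAP.** Section 8.8 restricts subgroup analysis to the three primary endpoints. Section 8.14, on additional endpoint analyses, is marked not applicable, and 8.7 plans no sensitivity analysis. No section explains the narrower list.

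**Step 3. See what follows about event counts.** Neither document states an expected rate for any outcome, and protocol 17.8 and SAP 7 say that no power calculation was made. There is no figure to reproduce. One ordering follows from the definitions alone. SAP 8.6 counts as an RFS event a target lesion recurrence from Visit 4, a new non-target lesion from Visit 3, or death from any cause. At patient level, therefore:

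RFS events ≥ max(target lesion recurrence events, deaths).

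OS cannot be ranked against recurrence. For illustration, take 1,500 patients (the upper figure in protocol 4.0) and assumed five-year risks that are not in the documents:

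- Recurrence 10%, death 30%: 1,500 × 0.10 = 150 recurrences and 1,500 × 0.30 = 450 deaths. RFS has at least 450 events.
- Recurrence 30%, death 20%: 1,500 × 0.30 = 450 recurrences and 1,500 × 0.20 = 300 deaths. RFS again has at least 450 events.

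Over assumed ranges of 5–40% for recurrence and 10–60% for death, the order of OS and recurrence goes both ways. The binary outcomes cannot be placed either: assumed failure rates of 1% to 20% give 15 to 300 failures.

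**The case against.** The best case for the SAP has four parts.

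- **The scope is coherent.** SAP 8.10 models exactly the three primary endpoints, and 8.8 limits subgroups to the same three. This is a plausible reason, but the SAP does not state it, and protocol 17.5 draws no line between primary and secondary outcomes.
- **The protocol leaves methodology to the SAP.** Section 17.9 defers the full methods to it, including multiple lesions, variable selection, data reduction and subgroups. Section 17.1, however, describes the SAP as a supplement to the protocol's statistical section. Deferring the method does not amount to permission to remove outcomes.
- **The commitment is thinner for RFS and OS.** This stands. Protocol 4.0 and 17.9 promise only time-to-event analyses for them, and SAP 8.6 supplies Kaplan-Meier estimates. The modelling commitment for these two rests on 17.5 alone, so secondary efficacy is the clearest contradiction. A reader might infer that the SAP drops the survival outcomes altogether. It does not; only their covariate models are absent.
- **Later analyses are possible.** Protocol 17.8 foresees further ad-hoc analyses, and SAP 8.1 allows documented departures in the final analysis. A reader might infer that the registry could never relate parameters to survival. That goes too far, since the data remain available. What is missing is pre-specification, and these provisions do not supply it.

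**Conclusion.** The inconsistency is real and should be corrected. Three of the six outcomes that the protocol undertakes to model have no covariate model in the SAP, and no reason is given. It is not a critical defect, because the models are exploratory and no confirmatory claim depends on them.

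The conclusion rests on the wording of the two documents and on no assumed rate. The table shells are a separate document that was not available, but layouts would not supply a method that the SAP text lacks.

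Two stronger readings are not supported. A reader might infer that the SAP leaves out the outcomes with the most events and keeps those with the fewest. Only the RFS ordering in Step 3 follows from the documents. Secondary efficacy, which is left out, is confined to re-ablated patients or lesions and may itself be sparse. A reader might also count RFS and OS as half of the modelling commitment. They are a third; the half is reached only with secondary efficacy.

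**What to change.** Before database lock, add to SAP 8.10:

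1. Cox models for RFS and for OS, with the same candidate ablation, patient and provider parameters as the recurrence model, adjusted for disease type and baseline ECOG. Adjusting for these is a recommendation, not a protocol requirement.
2. Child-Pugh score only within the patients to whom it applies. It is recorded only where applicable, and SAP 8.11 rules out imputation, so including it in a model for all patients would drop the rest.
3. A secondary efficacy model, fitted only if the number of unsuccessful repeat ablations allows it, with that condition written down in advance.
4. A statement that all of these are exploratory.

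If the sponsor no longer intends these models, amend protocol 4.0, 17.5 and 17.9 so that the stated modelling matches the SAP, and say why.

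The first route costs SAP wording and a few more models, with no new data items; the drawback is more exploratory estimates to label and interpret with care. The second route costs a protocol amendment and narrows what the registry undertakes to answer.

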19.0 DATA HANDLING AND RECORD KEEPING

19.1 Data Elements

The following three categories of data will be captured in the registry database: (1) ablation procedure parameters, (2) patient parameters, and (3) healthcare provider parameters. The complete list of data parameters requested for this registry database are listed below.

1. Ablation procedure parameters:

- a) Procedure type: laparoscopic surgical; open surgical; percutaneous.
- b) Complete procedure duration from start of anesthesia administration (start time) to completion of the procedure (end time).
- c) Ablation duration for each individual ablation attempt (minutes and seconds).
- d) Ablation duration, defined as the time elapsed between first ablation probe puncture and removal of the last probe at the completion of the ablation.
- e) Type of anesthesia used during ablation procedure.
- f) Anatomical location of ablation.
- g) Liver stiffness near ablation site, if obtained prior by ultrasound or MRI.
- h) Smallest ablation margin, if available. Note: if less than 5mm margin, include reason (vessel, duct, location, bowel, other).
- i) Ablation Zone measurement, if available
- j) Use of hydrodissection during ablation procedure.
- k) Type of probe(s) (including serial number).
- l) Number of probes.
- m) Maximum probe temperature, per probe (°C).
- n) Power settings used per probe (Watts).
- o) Constant power vs ramp-up.
- p) Number of probe placement attempts per probe (to get the probe in position).
- q) Number of changes in probe placement throughout the ablation (after energy has been delivered).
- r) Location of probe placement relative to the target lesion (central, peripheral).
- s) Tract ablation (yes/no).
- t) If overlap of coagulation zones, provide overlap, if available.
- u) Needle navigation/placement guidance method used.
- v) Image fusion details, if applicable
- w) Identify if ablation procedure guidance software was used (i.e. for target identification, ablation monitoring, and/or ablation confirmation)
 - If NeuWave ablation confirmation software used, note use of the software, tissue contraction percentage, and the software version
 - If other software, note supplier/manufacturer
- x) If applicable, total number of CT and Xray scans used for the Ablation and total amount of radiation dose
- y) Imaging details (contrast, slice thickness if applicable).

2. Patient parameters:

- a) Patient lesion details at baseline:

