This registry will be open to receiving data from all patients who are ablated with microwave ablation of soft tissue liver lesions using the NEUWAVE Microwave Ablation System. Given that the objective of the registry is to investigate the relationships that exist between the stated clinical outcomes, patient and provider parameters, and microwave ablation (MWA) time and power, no power analysis or sample size determination have been performed given the absence of a specific hypothesis to test.

8 Statistical Analysis Methods

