8.4.1 Primary Endpoint

Perioperative endpoint-

1. Technical success, defined as ablation of the target lesion(s) according to the protocol and covered completely, with an adequate margin, as defined by the performing physician (i.e., the ablation zone completely overlaps or

encompasses the target lesion(s) plus an ablative margin), as assessed by CT, MRI, PET, US, and/or X-ray, immediately following the procedure. Technical Success is assessed at Visit 2 following the ablation of the target lesion.

Short term endpoint -

2. Technique efficacy, ablation of the target lesion(s) according to the protocol and covered completely, with an adequate margin, as defined by the performing physician (i.e., the ablation zone completely overlaps or encompasses the target lesion(s) plus an ablative margin), as assessed by CT, MRI, PET, US, and/or X-ray, at Visit 3 (between 7 days and less than 3 months post-ablation).

Long term endpoint -

3. Target lesion recurrence (local recurrence) rate evaluated at every visit starting from visit 4 after the primary ablation at visit 2 of the target lesion(s), and overall evaluation at the 5-year follow-up, as assessed by CT, MRI, PET, US, and/or X-ray.

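### SAP 8.10 leaves measured ablation margin and ablation zone eligible as predictors of outcomes defined by margin coverage; if selected, they would attenuate the time and power effects

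*SAP*

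**What the plan says.** SAP 8.10 (Exploratory Analyses) will use logistic regression to "explore the relationship between dichotomous clinical outcomes (technical success and technique efficacy) and ablation procedure, patient, and provider parameters". On selection it says only this: "Significance level of 0.2 will be used for variable selection in a regression model". It adds a Cox model relating target lesion recurrence to the same three groups of parameters. No covariate is named, forced in or ruled out.

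Protocol 19.1 (Data Elements) sets out what belongs to each group and presents its list as complete. Under ablation procedure parameters it has the duration of each ablation attempt (1c), the overall ablation duration (1d) and the power setting per probe (1n). The same group contains "Smallest ablation margin, if available" (1h) and "Ablation Zone measurement, if available" (1i).

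SAP 8.4.1 defines technical success and technique efficacy alike: the ablation zone must cover the lesion, in the sense that it "encompasses the target lesion(s) plus an ablative margin". SAP 8.5 scores both as the performing physician's judgement that the ablation was complete.

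The Sample Size Justification (SAP 7, repeated in Protocol 17.8) gives the aim as relating clinical outcomes to "patient and provider parameters, and microwave ablation (MWA) time and power".

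**The concern.** Power and time are inputs. Zone and margin are what those inputs produce, and whether the zone covers the lesion with a margin is the substance of both success endpoints. A model that holds margin and zone fixed no longer asks whether more energy makes success more likely. It asks whether energy matters among lesions that ended with the same margin. That answer can be close to null even when the settings matter a great deal.

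The registry is meant to support guidance on ablation parameters, and Protocol 5.0 says that time, power and probe settings have not been studied systematically. SAP 8.10 is where outcomes are related to time and power. If margin enters those models, the report could conclude that settings matter little and margin matters much. For the success endpoints that is close to circular, and it says nothing about settings.

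**Working it through.** **1. Does the text admit the two items?** SAP 8.10 names the class of ablation procedure parameters. Protocol 19.1 defines that class and includes 1h and 1i. Protocol 17.9 leaves variable selection and data reduction to the SAP, which supplies only the 0.2 level. Read literally, both items are eligible. Nothing separates settings from measurements taken after energy delivery, and SAP 8.7 plans no sensitivity analysis that would expose the effect.

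**2. What happens if they are selected?** The documents give no power or event figure for these models, so there is nothing of the plan's own to reproduce. All inputs below are assumptions, apart from n = 1500, which is the planned maximum in the protocol summary. Energy E is one index standing for time and power, in SD units.

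- Zone (mm) = lesion size + 10 + 4E − 0.2(size − 20) + noise with SD 5.
- Margin = (zone − size)/2, so E moves the margin by 2 mm per SD and the residual SD is 2.5 mm.
- Success if margin + judgement noise (SD 2 mm) exceeds 1 mm, which gives about 85% success.
- Measured margin = margin + error with SD τ.

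Without margin in the model, the slope of E on the probit scale is 2/√(2.5² + 2²) = 2/√10.25 = 0.625. With measured margin in the model, let f = τ²/(6.25 + τ²). The slope is then 2f/√(6.25f + 4). The odds ratio is approximately exp(1.81 × slope), where 1.81 = π/√3 is the usual probit-to-logit scaling.

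| Model for success (lesion size always included) | f | Slope of E | OR per SD of E |
|---|---|---|---|
| No margin | – | 0.625 | 3.1 |
| Margin, error 1 mm | 0.138 | 0.276/√4.862 = 0.125 | 1.25 |
| Margin, error 2 mm | 0.390 | 0.780/√6.439 = 0.308 | 1.75 |
| Margin, error 3 mm | 0.590 | 1.180/√7.689 = 0.426 | 2.16 |
| Margin, no error | 0 | 0 | 1.00 |
| Margin, error 1 mm, plus a direct energy effect of 0.5 mm per SD | 0.138 | (0.276 + 0.5)/√4.862 = 0.352 | 1.89 |

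In the last row the odds ratio without margin is about exp(1.81 × 2.5/√10.25) = 4.1. Simulation of the same set-up agrees:

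- The OR was about 3.1 without margin, 1.25 at 1 mm error, 1.74 at 2 mm, 2.13 at 3 mm, and 1.93 with the direct effect.
- The measured margin reached p<0.2 in every run at 1 mm error.
- Energy reached p<0.2 in all runs without margin, in 67–74% with 1 mm error, in all runs at 2 and 3 mm, and in about 20% with an error-free margin. The last figure is what a 0.2 threshold gives a null variable.

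**3. A second set-up, with actual backward selection at 0.2.** Here energy is correlated with lesion size, both margin and zone are candidates, margin is recorded without error and, except in the last row, carries the whole energy effect. There were 200 runs per scenario, with 90% success unless stated.

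| Scenario | OR of E without margin and zone | OR with both | Margin kept | Energy kept |
|---|---|---|---|---|
| n = 1500, low / medium / high judgement noise | 7.2 / 3.8 / 2.2 | 0.98 / 1.01 / 1.03 | 99–100% | 23–27% |
| n = 500, same three noise levels | 7.4 / 3.9 / 2.2 | 1.00 / 1.01 / 1.03 | 85–100% | 19–26% |
| n = 1500, margin and zone available in half | 3.7 | 1.00 | 100% | 29% |
| n = 1500, 97% success | 4.1 | 0.99 | 98% | 23% |
| n = 1500, energy also acts outside the margin | 6.1 | 1.8 | 100% | 95% |

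**4. Missing values.** Items 1h and 1i are recorded only where available, and SAP 8.11 rules out imputation. A regression that includes either one ordinarily drops every patient or lesion without it. The attenuation is then joined by restriction to complete cases.

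**The case against.** Several stronger readings are tempting, and the documents do not support them.

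- **That the SAP puts margin and zone in the models.** It does not say so. Protocol 19.1 is a data-capture list, the primary objective speaks of selected parameters, and Protocol 5.0 describes procedure parameters as time, power and probes. An analyst could leave 1h and 1i out without contradicting the SAP. The two items are eligible, no more. However, the Protocol 5.0 list is introduced as examples while the 19.1 list is presented as complete, and two usages in one protocol are a reason to name the covariates.
- **That the time and power effects would be adjusted away.** That needs full mediation and a nearly error-free margin. With 2 or 3 mm of measurement error, or an energy effect outside the margin, the loss is partial and energy is still selected in nearly all runs.
- **That margin is literally the outcome.** Success is the physician's judgement, no millimetre threshold is set, and item 1h allows for margins under 5 mm with a reason. Technique efficacy is judged later, at Visit 3. Margin is close to the definition but does not determine the result.
- **That the Cox model is circular too.** Target lesion recurrence is not defined by margin, so margin is a legitimate prognostic factor there and a possible mediator. SAP 8.5 also excludes technique-efficacy failures from that analysis.
- **That SAP 8.10 is the only analysis serving the primary objective.** SAP 8.8 compares all three primary endpoints by disease type and by confirmation software use. Patient and provider parameters are also part of the stated aim.

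These points limit the claim and its severity. They do not remove the gap: the predictor class as written contains near-definitional measurements taken after energy delivery, and nothing in the SAP keeps them out.

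**Conclusion.** The point holds in conditional form. SAP 8.10 draws its candidates from a class that includes margin and zone, and does not exclude them from models of technical success and technique efficacy. Under the assumed inputs, selection of margin at 0.2 is likely: 85–100% of runs with backward selection, across all scenarios. If it is selected, the time and power effects are attenuated, for example from an odds ratio of 3.1 to between 1.25 and about 2.2 as margin error goes from 1 to 3 mm. They nearly vanish only when margin carries the whole effect and is measured with little error.

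The sizes rest on assumed effect, noise and error values, not on registry data; the direction follows from the definitions. For recurrence the issue is mediation alone, and no Cox model was simulated.

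Severity is should-fix. The models are labelled exploratory, no hypothesis is tested, and the primary endpoint estimates in SAP 8.5 do not depend on them.

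**What to change.** In SAP 8.10, before database lock:

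1. List the candidate predictors. For the main time and power models, use patient, lesion and provider parameters plus device settings and delivered time and power.
2. State that items 1h and 1i of Protocol 19.1 are not candidate predictors of technical success or technique efficacy.
3. Treat other measurements taken during or after energy delivery in the same way, for example maximum probe temperature (1m), placement changes after energy has been delivered (1q) and zone overlap (1t).
4. For target lesion recurrence, report time and power effects from a Cox model without margin and zone. If margin is of interest, fit it in a separate model labelled as such.

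The cost is a short SAP edit with an explicit covariate list, and no new data. The downside is fewer candidate variables and one extra labelled model. One limit remains: Protocol 19.1 records time as delivered duration and not as a preset, so the time effect still describes what was done and not what was planned.
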